### **10.3.2. Pharmacokinetic Analyses**

#### **10.3.2.1. Pharmacokinetic Analyses**

Pharmacokinetic parameter estimates for LY3316531 will be calculated using standard noncompartmental methods of analysis.

The primary parameters for analysis will be  $C_{max}$  and AUC of LY3316531. Other noncompartmental parameters, such as half-life, apparent clearance, absolute bioavailability, and apparent volume of distribution may be reported. Mean and individual plasma concentration

versus time profiles and individual and summary statistics of PK parameter estimates by treatment group will be generated.

Population-based methods of analyses may also be performed, to understand factors that influence the PK, characterize the inter- and intra-subject variability in PK and support simulations of multiple dose administration.

#### **10.3.2.2. Pharmacokinetic Statistical Inference**

The dose proportionality of selected LY3316531 PK parameters following IV administration in Part A of the study, including logarithm of  $C_{max}$  and relevant AUC values, will be examined across the entire dose range using a power-model approach (Smith et al. 2000). Other analyses of PK parameters may be performed as deemed appropriate.

#### **10.3.3. Pharmacodynamic Analyses and Clinical Activity**

Clinical activity and PD data obtained will be documented in the study report by dose, plasma drug concentrations, and time from dose. However, the data collected at the visits leading up to and including the Week 4 visit will be the data used for evaluation of changes in clinical activity and PD measures. Figures showing values of potential PD markers versus time will be created for each dose, with a line for each patient. Absolute percentage change from baseline for all will be summarized by providing the mean, standard deviation, median, minimum, and maximum for each cohort and overall for each sample day/time combination and maximum over the entire study. Data may be log-transformed prior to summarizing if necessary. The interpatient and intrapatient variability in human PD responses may also be assessed if appropriate.

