### Treatment Arms and Planned Duration for an Individual Patient/Subject:

**Part A (Single-Ascending Dose [SAD] in Healthy Subjects):** After a screening period up to 28 days, eligible subjects will be randomized to receive a subcutaneous (SC) or intravenous (IV) dose of LY3316531 (3 mg IV, 15 mg IV, 75 mg IV, 300 mg IV, 300 mg SC, 900 mg IV, or 2000 mg IV [planned dose]) or placebo (IV) on the morning of Day 1. Subjects will remain in the CRU for 24 hours after study drug administration and attend scheduled visits at the CRU for 12 weeks to assess the measurements for safety, tolerability, and PK. Sentinel dosing for the first 2 subjects of Cohorts 1 and 2 will be performed with 1 subject receiving LY3316531 and the other receiving placebo in a blinded manner.

**Part B (Multiple-Dose in Healthy Subjects):** After a screening period up to 28 days, eligible subjects will be randomized to receive a planned IV dose of LY3316531 (2000 mg [planned dose]) or placebo on the morning of Days 1, 29, and 57. The planned dose of 2000 mg LY3316531 may be adjusted based on safety, PK, and target-engagement data obtained in Part A of the study. An optional SC or IV second multiple-dose cohort will be determined after reviewing the data from the first cohort.

Subjects will remain in the CRU for 24 hours after receiving each dose of study drug and attend scheduled visits at the CRU for 12 weeks following the final (third) dose of LY3316531 to assess the measurements for safety, tolerability, and PK.

**Part C (Single-Dose in Patients with Psoriasis):** After a screening period up to 35 days, eligible patients with psoriasis will be enrolled to receive a single dose of LY3316531 on the morning of Day 1. Patients will receive 300 mg IV in Cohort 1 or, in the 2 optional cohorts, receive either a SC or IV dose (to be determined) not to exceed the maximum tolerated dose in Part A or the highest dose previously evaluated in healthy subjects. Patients will remain in the CRU for 24 hours after study drug administration and attend scheduled visits at the CRU for 16 weeks following administration of the study drug to assess the measurements for safety, tolerability, PK, and PD. Patients who respond to LY3316531 therapy will enter an extended follow-up period, which requires monthly visits up to Week 52. Patients who enter the extended follow-up period should be discontinued from the study when additional therapy becomes necessary (as determined by the investigator and patient).

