Exposure-response relationships for clinical activity measures in psoriasis (such as PASI score, static Physician Global Assessment, and body surface area) and safety endpoints will be investigated initially using graphical methods. Modeling approaches that relate exposure to the response at various time points or longitudinal models that relate the time course of exposure to the time course of response may be explored.

**Statistical:** PK/PD analyses will be conducted on data from all patients/subjects who receive at least 1 dose of the IP and have evaluable PK. Placebo data from all cohorts will be pooled across all dose-escalation cohorts for the purpose of analysis. Clinical activity and PD analyses will be conducted for all patients with psoriasis who receive the study drug (Part C only). Pharmacodynamic parameters, and their change from baseline, will be summarized at each applicable visit using descriptive statistics (number of subjects, mean, standard deviation, median, minimum, and maximum for continuous variables and number of subjects, frequency, and percent for categorical variables). No statistical inferences will be made and no control for multiplicity is planned. Additional analyses may be performed.

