### **5.1.3. Part C (Single-Dose Design in Patients with Psoriasis)**

One planned single-dose cohort will be enrolled to receive IV administration of LY3316531 with the option of 2 subsequent cohorts where the dose levels and route of administration (SC or IV) would be determined after reviewing the data from the first IV cohort.

The first cohort is planned to receive 300 mg of LY3316531 pending the analysis of available safety data from Part A. The safety scenarios for AEs, SAEs, and adverse laboratory abnormalities described in Section 7.4.2 that would prevent dose escalation in Parts A and B are the same that would prevent initiation of Part C. The actual starting dose and expected exposure will not exceed the dose/exposure that is concurrently being evaluated in Part A. Any available preliminary PK data from Cohorts 1, 2, and 3 (through Day 29) in Part A will be considered in the decision to initiate Part C as well.

Similarly, the dose for the optional cohorts will be determined based on cumulative data from previous cohorts, but will not exceed 2000 mg of LY3316531. Section 7.4.1 provides detailed information on how dose levels for the 2 optional cohorts will be determined and when the cohorts will begin enrollment procedures.

All patients who respond to LY3316531 treatment by exhibiting at least 50% reduction from baseline Psoriasis Area and Severity Index (PASI) score at Week 12 (Visit 11; Day 85) can enter an extended follow-up period for up to 52 weeks post-treatment administration (see Section 2.3). Other subjects who do not meet the above criterion for PASI reduction should be considered for discontinuation from the study at Week 16 (Visit 12; Day 113). Exceptions could be considered after a discussion between the sponsor and investigator.

A patient's participation is considered as complete if he/she received the study drug and completes all activities up to and including at least Day 85. Patients may be replaced if PK or PD data are not collected up to and including Day 85.

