## 7.4. Dose Modification

### 7.4.1. Dose Decision (Part C)

The decision to initiate the first patient cohort in Part C will be based on the trial-level safety review for Cohort 3; however, any available preliminary PK data from Cohorts 1, 2, and 3 (through Day 29) in Part A will be considered as well. Progression to the optional cohorts in Part C will occur when at least 4 weeks of clinical activity data (PASI scores) are available from at least 7 patients in the preceding cohort. In addition to the PASI scores, any available PK and applicable safety data from Part A will be considered for determining the dose for the optional patient cohorts. Dosing at the current level and further dose escalation will be discontinued if any of the scenarios described in Section 7.4.2 occur.

CCI

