##### **10.3.3.1. Pharmacokinetic/Pharmacodynamic Analyses**

Analyses of the relationship between LY3316531 exposure and efficacy endpoints collected in Part C (such as PASI score, sPGA, and BSA) will be investigated initially using graphical methods. Modeling approaches that use a simple direct response relationship (using AUC) or longitudinal models that link the time course of LY3316531 concentrations to the time course of response may be explored.

Analyses of the relationship between LY3316531 exposure and total CGRP serum concentrations will also be conducted using graphical- and model-based approaches. Additional PD endpoints and safety endpoints may be explored for exposure-response relationships if warranted upon review of the data.

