## Overview

Protocol I9H-MC-FFAA, A Phase 1 Randomized, Placebo-Controlled Study of LY3316531 in Healthy Subjects and an Open-Label, Single-Dose Study in Patients with Psoriasis has been amended. The new protocol is indicated by Amendment (b) and will be used to conduct the study in place of any preceding version of the protocol.

The overall changes and rationale for the changes made to this protocol are as follows:

The number of patients to be enrolled in the planned and 2 optional cohorts of Part C was decreased from 8 patients to a minimum of 7 patients. A minimum of 7 patients are required to complete a cohort but up to 8 patients would still be allowed if 8 eligible patients can be identified in a timely manner. The reduced minimum required sample size was deemed sufficient to assess if there is evidence of clinical activity of LY3316531 based on PASI scores at 4 weeks, and is adequate for assessment of safety, tolerability and PK of the compound in the patient population at this stage of development.

Decreasing the cohort size to 7 patients will facilitate analysis of PASI scores for the purpose of determining if an optional cohort is needed to proceed once 4 weeks of data have been collected from 7 patients in a preceding cohort, thus preventing delay if 8 eligible patients cannot be identified in a timely manner. This overall decrease in cohort size from 8 patients to 7 patients has resulted in the specific changes outlined below. The rationale described for the overall change applies to these specific changes.

- Section 1 Protocol Synopsis
  - Number of Patients/Subjects
    - Part C: The number of patients from which evaluable data will be obtained was changed from 24 patients to up to 24 patients (total number of patients for planned and optional cohorts).
    - Part C: The number of patients per cohort was changed from 8 patients to a minimum of 7 patients planned but up to 8 patients allowed per cohort.
- Section 5 Study Design
  - 5.1 Overall Study Design

- Table FFAA.5.1. Title was changed from “Summary of Patient/Subject Cohorts” to “Summary of Maximum Number of Patients/Subjects per Cohort” to reflect the planned number of subjects are the maximum number per cohort
- Table FFAA.5.1.1 Summary of Maximum Number of Patients/Subjects per Cohort Part C: Footnote c was added to Patient Cohorts 1, 2, and 3 to explain that a minimum 7 patients are planned but up to 8 patients are allowed per cohort.

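### Does the protocol's Week 4 sentence exclude later visits from the evaluation of clinical activity and PD change?

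*Protocol*

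**What the plan says.** Protocol 10.3.3 begins by saying that clinical activity and PD data will be documented in the study report. It then adds, of those measures, that "the data collected at the visits leading up to and including the Week 4 visit will be the data used for evaluation of changes". Later in the same paragraph it plans percentage change from baseline for each cohort and "overall for each sample day/time combination and maximum over the entire study".

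The synopsis has no Week 4 limit: "Pharmacodynamic parameters, and their change from baseline, will be summarized at each applicable visit using descriptive statistics". Protocol 10.3.3.1 adds that "longitudinal models that link the time course of LY3316531 concentrations to the time course of response may be explored".

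Four weeks of data has a stated use in two other places. Protocol 7.4.1 says "Progression to the optional cohorts in Part C will occur when at least 4 weeks of clinical activity data (PASI scores) are available"; the minimum is 7 patients in the earlier cohort. The amendment (b) rationale in Appendix 7 calls the smaller cohort "sufficient to assess if there is evidence of clinical activity of LY3316531 based on PASI scores at 4 weeks".

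The SAP summarises sPGA, PASI and BSA over time (9.4.1.1 to 9.4.1.3) and the PD biomarkers by treatment and timepoint (9.4.2), with no Week 4 limit. SAP 3 gives the SAP precedence over the protocol's statistical considerations and undertakes to identify substantial differences. SAP 11 reports none.

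On response, the synopsis says "Patients who respond to LY3316531 therapy will enter an extended follow-up period, which requires monthly visits up to Week 52", and protocol 5.1.3 defines those patients as "exhibiting at least 50% reduction from baseline Psoriasis Area and Severity Index (PASI) score at Week 12". The PASI categories in SAP Table 2 and 9.4.1.2 are 75, 90 and 100.

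**The concern.** Taken at face value, the Week 4 sentence closes the evaluation of change at Day 29. Part C follows patients to Day 113, and responders to Week 52. Week 12, which decides entry to extended follow-up, would fall outside the window. That does not fit the whole-study summaries in the same paragraph, or the provision in 5.1.3 that patients may be replaced if PD data are not collected to Day 85.

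The SAP then includes the later visits without comment while stating that nothing changed. If the literal reading were the intended one, a reader of the report could not tell whether activity was to be judged at Week 4 or across follow-up. Choosing between the two after seeing the data would be a real, if modest, weakness.

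The PASI 50 point compounds this. A patient who improves by 60% counts as a responder for extended follow-up but as a non-responder in every category the SAP tabulates.

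**Working it through.** The plan gives no figure to reproduce, so the check is a count of visits followed by a comparison of readings.

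**Visits a literal window would leave out** (Part C schedule, protocol 2.3; extended visits numbered up to Visit 20 in APP.6.3)

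- Numbered post-dose visits V3 to V12: Days 4, 8, 15, 22, 29, 43, 57, 71, 85, 113, which is 10 visits.
- After Day 29: V8 to V12 (Days 43, 57, 71, 85, 113), which is 5 of 10.
- For a patient followed to Visit 20, V13 to V20 add 8: (5 + 8) / (10 + 8) = 13 of 18.
- Time from the end of the window: 85 - 29 = 56 days to Week 12; 113 - 29 = 84 days to Week 16.

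These are visit counts. Not every measure is taken at every visit, so they overstate the assessments affected.

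**What each reading would produce**

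| Reading of the Week 4 sentence | Summaries under the protocol | Summaries under the SAP |
|---|---|---|
| Limits every analysis of change to Day 29 | Conflicts with the rest of 10.3.3 and the synopsis | All timepoints, because the SAP takes precedence |
| Marks an early read-out, or the data for the cohort decision | All timepoints, with Week 4 used for the decision | All timepoints |

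The right-hand column is the same in both rows. Whichever reading is taken, an analyst who follows the SAP produces the same descriptive tables.

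**Which reading fits better.** The second agrees with 7.4.1, with the amendment (b) rationale, and with the rest of 10.3.3. It also agrees with protocol 10.3.6 and SAP 10. These time the analysis for the study report to the point when Part C patients have finished their requirements up to Day 113 or left early, and apply all planned analyses to the available data. Later results may go into an addendum. An analysis timed to Day 113 sits badly with a plan to discard everything after Day 29.

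**PASI 50.** The gate is at least 50% improvement and the lowest tabulated category is at least 75%, so patients from 50% to under 75% are not counted separately. But SAP 9.4.1.2 already summarises percent improvement over time and lists it by patient and timepoint. With 7 or 8 patients per cohort, the number at or above 50% at Week 12 can be counted directly from the listing. One patient is 1/8 = 12.5 or 1/7 = 14.3 percentage points.

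**The case for a change.** The strongest case for a change has three parts.

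First, the benign reading is inferred. Protocol 10.3.3 does not refer to 7.4.1. The progression rule there names PASI only, whereas the Week 4 sentence covers PD measures too. The sentence is also set in contrast to what the report will document, so it can be read as a rule for the report. This stands as a drafting criticism: neither document states the role of Week 4.

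Second, SAP precedence comes with an undertaking to identify substantial differences, and SAP 11 identifies none. Version lag is an unlikely excuse. The SAP was written against amendment (a), but the amendment (b) summary lists changes only in Sections 1, 5 and 7, so the Week 4 sentence was probably already there. This stands only on the literal reading. The SAP carries out the all-timepoint summaries that the synopsis and most of 10.3.3 call for, so reporting no change is defensible.

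Third, the 50% criterion is the only rule in either document for which patients respond to treatment, and SAP 9.1 limits summaries to those detailed. Data after Week 16 come mainly from patients who met that criterion, so its proportion would help readers. That is true. But the protocol never promises it, 5.1.3 uses it as an operational gate with exceptions allowed, and SAP Table 2 attaches clinical meaning to PASI 75. SAP 3 also allows supplementary analyses if the study report identifies them. Its absence contradicts nothing.

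**Conclusion.** No change follows. The Week 4 sentence is loosely drafted: it does not say what it governs, and on a literal reading it clashes with its own paragraph. The rest of the plan resolves the clash without guesswork. All scheduled assessments are summarised descriptively, and the 4-week PASI data serve the optional-cohort decision. Up to 5 of 10 numbered visits to Week 16 would be at stake on the literal reading, and none is lost under the SAP. The PASI 50 row is a reasonable option that needs no new data and corrects no error.

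This rests on two assumptions: that the SAP's precedence clause is applied as written, and that the table shells, which were not available, follow SAP 9.4. The measures are exploratory, Part C is open-label without a control, and no inference or multiplicity control is planned, so no primary or secondary result and no error rate depends on the point.

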##### **10.3.3.1. Pharmacokinetic/Pharmacodynamic Analyses**

Analyses of the relationship between LY3316531 exposure and efficacy endpoints collected in Part C (such as PASI score, sPGA, and BSA) will be investigated initially using graphical methods. Modeling approaches that use a simple direct response relationship (using AUC) or longitudinal models that link the time course of LY3316531 concentrations to the time course of response may be explored.

Analyses of the relationship between LY3316531 exposure and total CGRP serum concentrations will also be conducted using graphical- and model-based approaches. Additional PD endpoints and safety endpoints may be explored for exposure-response relationships if warranted upon review of the data.

##### **10.3.3.2. Health Outcome Measures for Subjects with Psoriasis**

The Patient's Global Assessment of Disease Severity will be reported and summarized at each applicable visit using standard descriptive statistics including number of subjects, mean, standard deviation, median, minimum, and maximum for continuous variables and number of subjects, frequency, and percentages for categorical variables. Comparisons between each active treatment and pooled placebo group will be made. Results from statistical analyses will be provided for descriptive purposes only; therefore, no statistical inferences will be made, and no control for multiplicity is planned.

#### ***10.3.4. Evaluation of Immunogenicity***

The frequency and percentage of patients/subjects with baseline ADA, with ADA anytime postbaseline, and/or with TE ADA to LY3316531 will be tabulated. For patients/subjects who are ADA negative at baseline, TE ADAs are defined as those with a titer 2-fold (1 dilution) greater than the minimum required dilution of the assay. For patients/subjects who are ADA positive at baseline, TE ADAs are defined as those with a 4-fold (2 dilutions) increase in titer compared to baseline. For the patients with TE ADA, the distribution of maximum titers will be described. The frequency and percentage of patients with neutralizing antibodies may also be tabulated for patients with TE ADA.

The relationship between the presence of antibodies and the PK parameters and PD response including safety to LY3316531 may be assessed.

#### ***10.3.5. Data Review During the Study***

Access to safety data is scheduled to occur after every dosing session. The purpose of these reviews is to guide dose selection for the next dosing session, and/or to inform the design of subsequent studies. The investigator and the Lilly sponsor team will make the determination regarding dose escalation, based upon their review of the data. The investigator will remain blinded, and the Lilly sponsor team will be unblinded during these reviews.

In addition, data snapshots for preliminary analyses of PK data are planned to occur after Day 29 of Cohort 3 (Part A) prior to the initiation of the multiple-dose cohorts (Part B). The evaluation of these data will aid in determining the dose, margin of safety, and adjustment of PK sampling schedule. Data snapshots are also planned to occur after Day 29 of Cohort 6 in Part A and Day 57 of Cohort 1 in Part B. Additional data snapshots may be conducted as required. These snapshots and analyses will be conducted while the trial is ongoing, but no changes to the study design are planned.

#### ***10.3.6. Interim Analyses***

An interim analysis will occur when all patients/subjects in Parts A, B, and C have completed all requirements stated in the Schedule of Activities (Section 2; up to Day 85 for Part A, up to Day 141 for Part B, and up to Day 113 for Part C) or discontinued early from the study. Lilly employees and employees of any third-party organization involved in the interpretation of data collected during the study are authorized to evaluate unblinded data for the interim analyses. This interim analysis will include all planned analyses of available data. The data will be used for the development of a clinical study report (CSR). Results that are not available at the time a CSR is developed can be provided in a separate report or CSR addendum.

## Appendix 1. Abbreviations and Definitions

---

Term	Definition
ADA	antidrug antibody
AE	adverse event: Any untoward medical occurrence in a patient or clinical investigation subject administered a pharmaceutical product that does not necessarily have a causal relationship with this treatment. An AE can therefore be any unfavorable and unintended sign (including an abnormal laboratory finding), symptom, or disease temporally associated with the use of a medicinal (investigational) product, whether or not related to the medicinal (investigational) product.
ALP	alkaline phosphatase
ALT	alanine aminotransferase
assent	Agreement from a child or other individual who is not legally capable of providing consent, but who can understand the circumstances and potential risks involved in participating in a study (required by some institutional review boards [IRBs]/ethical review boards [ERBs]).
AST	aspartate aminotransferase
blinding	A procedure in which 1 or more parties to the study are kept unaware of the treatment assignment(s). Unless otherwise specified, blinding will remain in effect until final database lock.  A single-blind study is one in which the investigator and/or his staff are aware of the treatment but the patient/subject is not, or vice versa, or when the sponsor is aware of the treatment but the investigator and/his staff and the patient/subject are not. A double-blind study is one in which neither the patient/subject nor any of the investigator or sponsor staff who are involved in the treatment or clinical evaluation of the subjects are aware of the treatment received
CGRP	calcitonin gene-related peptide
complaint	A complaint is any written, electronic, or oral communication that alleges deficiencies related to the identity, quality, purity, durability, reliability, safety or effectiveness, or performance of a drug or drug delivery system.
compliance	Adherence to all the study-related requirements, good clinical practice (GCP) requirements, and the applicable regulatory requirements.
confirmation	A process used to confirm that laboratory test results meet the quality requirements defined by the laboratory generating the data and that Lilly is confident that results are accurate. Confirmation will either occur immediately after initial testing or will require that samples be held to be re-tested at some defined time point, depending on the steps required to obtain confirmed results.
CRP	clinical research physician: Individual responsible for the medical conduct of the study. Responsibilities of the CRP may be performed by a physician, clinical research scientist, global safety physician, or other medical officer.
CRU	clinical research unit
CSE	clinically significant event

CSR	clinical study report
C-SSRS	Columbia-Suicide Severity Rating Scale
ECG	electrocardiogram
eCRF	electronic case report form
enroll	The act of assigning a patient/subject to a treatment. Patients/subjects who are enrolled in the study are those who have been assigned to a treatment.
enter	Patients/subjects entered into a study are those who sign the informed consent form directly or through their legally acceptable representatives.
ERB	ethical review board
GCP	good clinical practice
HBcAb	hepatitis B core antibody
HBsAb	hepatitis B surface antibody
HIV	human immunodeficiency virus
IB	Investigator's Brochure
ICF	informed consent form
ICH	International Council for Harmonisation
Ig	immunoglobulin
IL	interleukin
informed consent	A process by which a patient/subject voluntarily confirms his or her willingness to participate in a particular study, after having been informed of all aspects of the study that are relevant to the patient's/subject's decision to participate. Informed consent is documented by means of a written, signed, and dated informed consent form.
interim analysis	An interim analysis is an analysis of clinical study data, separated into treatment groups, that is conducted before the final reporting database is created/locked.
investigational product (IP)	A pharmaceutical form of an active ingredient or placebo being tested or used as a reference in a clinical study, including products already on the market when used or assembled (formulated or packaged) in a way different from the authorized form, or marketed products used for an unauthorized indication, or marketed products used to gain further information about the authorized form.
investigator	A person responsible for the conduct of the clinical study at a study site. If a study is conducted by a team of individuals at a study site, the investigator is the responsible leader of the team and may be called the principal investigator.
IV	intravenous

legal representative	An individual or judicial or other body authorized under applicable law to consent, on behalf of a prospective patient/subject, to the patient's/subject's participation in the clinical study.
mAb	monoclonal antibody
MTD	maximum tolerated dose
open-label	A study in which there are no restrictions on knowledge of treatment allocation, therefore the investigator and the study participant are aware of the drug therapy received during the study.
PASI	Psoriasis Area and Severity Index
PD	pharmacodynamic(s)
PK	pharmacokinetic(s)
PSS	Psoriasis Symptom Scale
PUVA	psoralen plus ultraviolet A light therapy
QTc	QT interval
randomize	The process of assigning subjects/patients to an experimental group on a random basis.
RNA	ribonucleic acid
SAD	single-ascending dose;
SAE	serious adverse event
SC	subcutaneous
screen	The act of determining if an individual meets minimum requirements to become part of a pool of potential candidates for participation in a clinical study.
SUSAR	suspected unexpected serious adverse reaction
TB	tuberculosis
TBL	total bilirubin level
TE	treatment emergent
TEAE	treatment-emergent adverse event: Any untoward medical occurrence that emerges during a defined treatment period, having been absent pretreatment, or worsens relative to the pretreatment state, and does not necessarily have to have a causal relationship with this treatment
Th	T helper
TNF	tumor necrosis factor

**TST** tuberculin skin test

**ULN** upper limit of normal

